6.9 Limitations of the Study

The number of patients for this study is too small to definitively demonstrate safety or effectiveness of the treatment. Since all the possible variables that might affect the outcome of this treatment are not known at this point, the results may vary. However, this study may give indications of the safety and value of this treatment method, as well as provide information and data necessary to undertake a larger clinical trial.

6.10 Safety Monitoring and Reporting of Adverse Events

A Data Safety Monitoring Board (DSMB) consisting of independent physicians, who are not investigators in the study, nor have a perceived conflict of interest with the conduct and administration of the investigation, may be convened to evaluate investigation progress and review adverse events.

An independent Clinical Events Committee (CEC) consisting of physicians, who are not investigators in the study, nor have a perceived conflict of interest with the conduct and administration of the study, may be established to adjudicate clinical events reported during the study. This adjudication will be performed according to standard operating procedures to assess whether the events were due to a pre-existing or unrelated condition, procedure-related, technique-related, and/or product-related.

Regularly scheduled monitoring, including on-site visits, will be conducted, in part, for identification of adverse events and assurance that they are accurately reported within the appropriate time frame.

Definitions for adverse events were derived from the ICH guideline on Clinical Data Safety Management: Definitions and Standards for Expedited Reporting, Section II: Definitions and

Terminology Associated with Clinical Safety Experience. Definitions are provided in Appendix D.

All adverse events (or adverse experiences), related or unrelated to the AMDC product or procedure, should be reported on the Event case report form within ten days of the site's knowledge of the adverse event.

All serious adverse events, serious adverse drug reactions, and suspected unexpected serious adverse drug reactions (SUSARs) related to the AMDC product or procedure shall be reported immediately to the data coordinating center (Cook Research Incorporated), who will inform the Sponsor accordingly. The immediate report should be made by the investigator within a very short period of time and under no circumstances should this exceed 24 hours following knowledge of the serious adverse event. SUSARs that are life-threatening or have been lethal will be reported, at the latest, within 7 days after the Sponsor becomes aware of them. All relevant information about the aftermath of this will be reported within a time period of another 8 days. Other reports of SUSARs will be made within 15 days after the Sponsor becomes aware of them.

All adverse events and adverse drug reactions will be investigated in collaboration with the Investigator involved as well as with the Principal Investigator, as needed (i.e. adjudication will be carried out according to predetermined procedures when necessary).

All adverse events that are not SUSARs, will be listed in the annual safety report, Development Safety Update Report (DSUR), according to the ICH E2F Guideline. The DSUR will be submitted annually to the assessing review committee and the competent authority. In accordance with regulatory requirements within each country, appropriate reports will be made to inform the investigators of adverse effects attributable to AMDC. The Investigator will be responsible for informing the local ethics committee accordingly, whereas the Sponsor will inform the competent authority according to reporting regulations.

7.0 Statistical Considerations

7.1 Sample Size Calculations

Fifty patients will be enrolled in this study. This population is sufficient to demonstrate the feasibility and potential efficacy of treatment and methods of AMDC delivery in patients with fecal incontinence. In addition, information concerning the safety of the treatment, likely complications, and potential utility of the cell therapy can be gathered with this population.

7.2 Analysis Plan

Endpoints will be summarized using frequency tables, means and standard deviations, 95% confidence intervals, and/or medians and ranges. Although it is expected that the study will

have too few patients, exploratory analyses of subgroups and covariates may be performed to investigate their relationship to AMDC treatment and to generate hypothesis and pilot data for future larger studies.

8.0 Deviations from Clinical Investigation Plan

Deviations or non-compliances will be recorded together with an explanation. Deviations that impact the rights, welfare or safety of patients shall be reported to the sponsor, regulatory authorities and Ethics Committee/REB as required.

The reasons for withdrawal and discontinuation of any patient from the study should be recorded, if possible. If such discontinuation is because of problems with safety or lack of effectiveness, that patient should still be followed-up in the study, if possible.

9.0 Safety Monitoring

All individual Investigators participating in the study are entitled to stop enrolling patients in case of disagreement with a delivered official decision by DSMB. If this should occur, the individual Investigator (Center) will not enroll any more patients, but will continue to follow those already enrolled according to the protocol. However, cases already included in the study remain in the population of cases analyzed.

10.0 Privacy, Confidentiality, and Ethical Considerations

Patient confidentiality will be maintained during the clinical study in a way to ensure that information can always be tracked back to the source data through patient enrollment number and patient initials (if available). Data relating to the study may be made available to third parties (as an audit performed by regulatory authorities) provided that data is treated confidentially and the patient's privacy is intact.

Study patients will be assigned a unique enrollment number, and will be identified to the Sponsor only by this unique enrollment number and patient initials. Only de-identified patient information will be collected by the Local or Central Monitor.

De-identified health information will be used by researchers involved in the study. "Researchers" include the patient's physician and the staff of collaborators, Investigators in other locations studying these products, representatives of Cook MyoSite (the Sponsor and Manufacturer), and representatives from Cook Research Incorporated to assist in research.

These data will be used to gain additional experience about these products, and to advance medical knowledge by making presentations and writing articles about the study. These data

may also be reviewed by government agencies that watch over research and approve medical products for use. If the product will be used in other countries, these data may be reviewed by similar agencies in those countries.

These data may also be combined with health information about other patients. The Sponsor or their designee will keep all the data in an ongoing database of information about the products so that information can be studied and analyzed. When the follow-up period of the study is over, no new information about individual patients will be added, but review of the data may continue. If a presentation is made, or reports and articles are written about this study, only de-identified information will be used.

For ethical considerations, all patients will be required to sign a consent indicating their willingness to participate and that they have been fully informed of the risks and benefits of participation. In addition, the study will be conducted under supervision of an ethical review committee and in compliance with the ICH Guidelines for Good Clinical Practice, the ISO 14155 and the Declaration of Helsinki.

11.0 Data Reporting and Record Retention

All study records and reports will be kept in accordance with applicable local and global regulations. The Sponsor will be notified before destruction (shredding) of these files.

Progress reports and a final report at the conclusion of the clinical study will be submitted by the Principal Investigators and Sponsor to the regulatory bodies as required by local regulations. All participating Principal Investigators will approve the Final Report. If an Investigator does not agree with the conclusion and will not sign the Final Report, (s)he must state the reasons for this. Until a Final Report has been formulated and approved by all of the participating Investigators, the Protocol and the study data are confidential and must not be published except for approved interim results. A copy of the Final Report will be sent to the Ethics Committees.

12.0 Publication Policy

The Principal Investigator and/or Institution shall furnish the Sponsor with a written copy of any proposed publication or presentation of material relating to the study at least thirty (30) days in advance of the date of the proposed first submission for publication or presentation. Within such thirty (30) day period, the Sponsor shall review the material and advise Principal Investigator and/or Institution as to whether it contains any confidential information which must not be disclosed and as to whether the proposed publication date is in conflict with Cook's publication strategy. If the material is deemed to contain confidential information, the Principal Investigator and/or Institution shall edit the material in accordance with the recommendation of Cook before publication or presentation. If the proposed publication date is in conflict with

Cook's publication strategy for the Study Product, Cook and Institution will negotiate a mutually agreeable publication date for the proposed publication.

In addition to the foregoing, in the event that the publication discloses patentable material, Principal Investigator and/or Institution shall grant Sponsor sufficient time, not to exceed ninety (90) days, to obtain proprietary rights protection for any material prior to publication or presentation. Cook's review of any proposed publication or presentation materials shall not relieve Principal Investigator and/or Institution from any of its obligations regarding confidential information. Any and all publications or presentations of material relating to the Study shall require the express written permission of the Sponsor, which will not be unreasonably withheld.

13.0 Data Collection

Data will be collected on a secure web-based electronic case report form (eCRF) and entered by qualified personnel.

Patient data will be collected and entered by the investigative site into an eCRF system. This is a secure, web-based system, allowing those with permission to access data from any location at any time. Site personnel are required to have unique login names and passwords in order to enter patient data, and, in accordance with 21 CFR Part 11, the eCRF system creates a secure, computer-generated, time stamped audit trail to record the date and time of operator entries and actions that create, modify, or delete electronic records.

14.0 Study Administration and Information

For additional contact information, please refer to Appendix E.

14.1 Study Administration

The study will be conducted in compliance with ISO 14155 and the International Conference of Harmonization Guideline for Good Clinical Practice. All cell and tissue processing will comply with quality standards specified in applicable local regulations.

14.4 Investigators

A current list of clinical investigators along with their contact and site information is provided in Appendix E. The contact information will be updated and maintained by the Data Coordinating Center.

14.5 Monitoring Arrangements

The conduct of the clinical trial will be supervised through a process of remote and on-site monitoring. The data coordinating center will be responsible for monitoring the study for adverse events. The possible adverse events associated with this study are listed in Section 6.10, Risk Analysis and Risk Assessment are discussed in Section 5.

Monitoring will verify that clinical study activities comply with relevant regulations. These activities shall be consistent with requirements as specified in the Declaration of Helsinki, International Conference on Harmonization, Good Clinical Practices, and other regulations in force in the country where the study takes place.

Monitoring will ensure:

- The study is being conducted in accordance with the protocol, relevant regulations and company policies
- Adequate protection of the rights and safety of informed human patients involved in the clinical study
- Quality and integrity of data
- Proper use, treatment, and attitude toward the investigational material and to observe the use of the material to learn the opportunities for improvement

The study will be monitored in accordance with written standard operating procedures. [REDACTED]

[REDACTED]

14.6 Data Management and Quality Assurance

Patient demographics, procedural information and follow-up data will be collected in a secure electronic database on standardized case report forms. All data are verified for accuracy and consistency, and all data edits are tracked with a verifiable audit trail.

[figure not shown]
15.0 Approvals and Agreements

The sponsor and the principal clinical investigators for each site shall agree to this document and any modifications. A justification for any modifications will be documented. Approval and agreement will be indicated by signing and dating this document.

APPENDIX A: Detailed Study Flow Diagram

¹ Previous exam results may also be used for the baseline assessments as long as they 1) were completed within 6 months prior to enrollment, 2) collected all required data, and 3) the patient did not undergo any procedures or change in condition since the exam that, in the physician's discretion, would be likely to invalidate the previous results.

APPENDIX B: Wexner Score

Wexner Score [1]

APPENDIX C: Fecal Incontinence Quality of Life Scale

Fecal Incontinence Quality of Life Scale (FIQL) [2]

A 12x12 grid of black bars. The first 11 columns are horizontal bars of varying lengths. The last column is a vertical stack of 12 horizontal bars. A dashed line is drawn across the grid.

A large black rectangular redaction box covers the majority of the page content, starting below the header and ending above the footer. It is positioned to the left of the main text area.

APPENDIX D: Definitions

Adverse Event or Adverse Experience

An adverse event (AE) is any untoward medical occurrence in a patient or clinical investigation subject administered a pharmaceutical or biologic product and which does not necessarily have a causal relationship with this treatment. An AE can therefore be any unfavorable and unintended sign (including an abnormal laboratory finding), symptom, or disease temporally associated with the use of a medicinal (investigational) product, whether or not related to the medicinal (investigational) product.

Adverse Drug Reaction

An adverse drug reaction (ADR) is any noxious and unintended response to a medicinal product related to any dose where there is a reasonable possibility of a causal relationship, i.e., the relationship cannot be ruled out.

Unexpected Adverse Drug Reaction

An adverse reaction, the nature and severity of which is not consistent with the applicable product information contained in the Investigators Brochure.

Serious Adverse Event or Serious Adverse Drug Reaction

Any events or drug reactions that, either due to their serious nature or due to the significant, unexpected information they provide, justify expedited reporting. A serious adverse event is defined as any event which meets any of the following criteria:

Death: An event, which results in the death of a patient.

Life Threatening Adverse Event: An event that if untreated, would lead directly to the death of the patient.

Hospitalization: An event that results in an admission to the hospital for any length of time.

Prolongs hospitalization: An event, which occurs while the study patient is hospitalized and prolongs the patient's hospital stay (due to potential disability, danger to life, or the event is terminal).

Causes persistent or significant disability or incapacity: An event that leads to a persistent or permanent disabling condition, congenital anomaly or birth defect.

Severity

Severity is a clinical determination of the intensity of a specific event. The event itself may be of relatively minor clinical significance. Severity is not the same as "serious", which is based on outcome or action criteria associated with events that pose a threat to a patient's life or functioning.

Suspected Unexpected Serious Adverse (Drug) Reaction

A serious adverse reaction, the nature and severity of which is not consistent with the applicable product information contained in the Investigator's Brochure. Serious refers to an event that meets any of the above-mentioned serious adverse event-criteria."

Relationship to AMDC

A determination will be made of the relationship (if any) between an adverse event and the AMDC treatment. The determination will be referred to a clinical events committee as needed. A causal relationship is present if a determination is made that there is a reasonable possibility that the adverse event may have been caused by the AMDC treatment. Adverse events meeting this criterion will be reported as an adverse drug reaction. If the event also meets one of the criteria for classification as "serious", it will be reported as a serious adverse drug reaction.

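### Appendix D gives its information-based ground for a serious event no criterion, and its test of unexpectedness is ambiguous, so some related reactions can miss expedited reporting

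*Combined protocol and SAP*

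**What the plan says.** Appendix D, entry on serious adverse events and serious adverse drug reactions: the opening sentence covers events or reactions that "either due to their serious nature or due to the significant, unexpected information they provide, justify expedited reporting". The next sentence gives the working rule: "A serious adverse event is defined as any event which meets any of the following criteria". Five criteria follow: death; a life-threatening event; hospitalization; prolonged hospitalization; and lasting disability or incapacity, which also takes in congenital anomaly and birth defect.

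Appendix D, Severity entry: seriousness is described as something "which is based on outcome or action criteria associated with events that pose a threat to a patient's life or functioning".

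Appendix D, entry on unexpected adverse drug reactions: "An adverse reaction, the nature and severity of which is not consistent with the applicable product information contained in the Investigators Brochure".

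Appendix D, SUSAR entry: "A serious adverse reaction, the nature and severity of which is not consistent with the applicable product information contained in the Investigator's Brochure". It adds: "Serious refers to an event that meets any of the above-mentioned serious adverse event-criteria".

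Section 6.10 sets the reporting routes. Sites enter every adverse event on the Event form within ten days. Serious events related to the product or procedure go to the data coordinating center within 24 hours. For onward reporting, "SUSARs that are life-threatening or have been lethal will be reported, at the latest, within 7 days" of the sponsor becoming aware, and other SUSARs are reported within 15 days. Events that are not SUSARs are listed in the annual DSUR.

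**The concern.** Which reporting clock runs for an event depends on two classifications made under Appendix D: whether the event is serious, and whether it is unexpected. Each has a weakness.

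For seriousness, the opening sentence names two alternative grounds, but no listed criterion corresponds to the second, the significant, unexpected information that an event provides. An event can therefore fit the stated purpose of the entry and still fail the rule that decides the class.

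For unexpectedness, the wording joins nature and severity with *and*. It does not say whether a departure in severity alone is enough. Two sites or two assessors could classify the same reaction differently.

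At stake are the speed at which such events reach the data coordinating center and the authorities, and for the first weakness the serious-event tally, in a 50-patient study whose primary objective concerns safety.

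**Working it through.** The plan gives no figure to reproduce. The check sets the definitions beside the reporting routes and follows two cases through them.

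**Which sentence controls seriousness.** Three places in Appendix D point to the list and not to the opening sentence. The Severity entry rests seriousness on outcome or action criteria. The SUSAR entry refers back to the listed criteria. The entry on relationship to AMDC calls a reaction a serious adverse drug reaction only if it meets one of those criteria. None of the three mentions the information ground.

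**Case 1: a related, medically important event that meets none of the five criteria.**
- Serious under the list: no.
- 24-hour site report (Section 6.10): not triggered. The ten-day Event form applies.
- SUSAR: no, because a SUSAR must be serious. If the event was also unexpected, the report lost is the 15-day one. The 7-day clock is not in play, since a fatal or life-threatening event would already meet the list.
- Onward route: annual DSUR.
- Serious-event tally: not counted. With 50 treated patients (Section 6.1), one such patient is 1/50 = 0.02, or 2 percentage points.
- Primary objective (Section 2.1): unaffected. It counts related adverse events whether or not they are serious.

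**Case 2: a related serious reaction of a type listed in the Investigator's Brochure, but more severe than listed.**
- Serious under the list: yes, by assumption.
- 24-hour site report: still due. Section 6.10 requires it for every related serious event, expected or not.
- SUSAR on the literal reading, where both nature and severity must differ: no, because the nature is consistent. The 7-day report (if life-threatening or fatal) or the 15-day report is lost, and the event goes to the annual DSUR.
- SUSAR on the looser reading, where the combined profile fails to match if either part differs: yes, and nothing is lost.
- Serious-event tally and primary incidence: unaffected on either reading, because expectedness plays no part in them.

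**Size by case.**

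| | Site report | Onward report | Serious tally |
|---|---|---|---|
| Case 1 | 24 hours becomes ten days | 15 days (if unexpected) becomes annual DSUR | 2 points per patient |
| Case 2, literal reading | unchanged at 24 hours | 7 or 15 days becomes annual DSUR | unchanged |
| Case 2, looser reading | unchanged | unchanged | unchanged |

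**The case against.** The strongest objection is to the second weakness. The wording has a singular verb, which suggests that nature and severity form one profile to be compared with the brochure, and a profile that departs on severity alone does not match. The unexpected-reaction and SUSAR entries use the same phrase, so they do not contradict each other. This stands: the wording is ambiguous, and a reader who infers that it plainly excludes worse-than-listed reactions goes further than the text. But nothing elsewhere in the protocol settles which reading applies.

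The list is also broad. The life-threatening criterion covers an event that would lead directly to death if untreated, hospitalization counts whatever its length, and lasting disability is included. A reader might infer that an injection-site abscess, a fistula or a new neoplasm managed without admission falls outside the list. The documents do not support that as a general statement, since some such events could meet one of these criteria. The gap exists only for events that meet none.

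Other provisions offer some protection. All adverse events reach the Event form within ten days and are investigated with the site. Section 6.10 calls for reports on effects attributable to AMDC under each country's requirements, and Sections 10.0 and 14.1 commit the study to GCP and ISO 14155. These reduce the practical delay but do not change how Appendix D classifies an event. The DSMB and the clinical events committee are optional, and the committee's adjudication as described in Section 6.10 addresses cause, not seriousness or expectedness.

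Finally, Section 6.10 says the definitions derive from an ICH guideline. That text is not in the documents, and nothing here depends on it.

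**Conclusion.** The point holds, in two parts of unequal weight.

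The first is an internal inconsistency. The serious entry states an information-based ground that its own criteria do not implement, and the SUSAR entry is tied to those criteria. A related event that meets only that ground loses the 24-hour site report and, if unexpected, the 15-day onward report. It is also missing from the serious-event tally. The 2-point figure assumes one affected patient among 50 treated. The documents give no frequency for such events, so no expected number can be stated.

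The second is an ambiguity. On the literal reading, a serious reaction that is worse than the brochure describes loses its 7- or 15-day onward report and nothing else.

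A reader might infer that both weaknesses delay the site report, or that they bias the primary result. Neither follows. The 24-hour rule does not depend on expectedness, and the primary incidence counts all related events. Sections 7.1 and 7.2 set no threshold or test on serious events. This is a gap in safety reporting that is cheap to close, and it does not undermine the study's main estimate.

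**What to change.** In Appendix D:

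1. Add a sixth criterion to the serious list that gives effect to the opening sentence: an event judged medically important because of the significant, unexpected information it provides.
2. State in the SUSAR entry that its reference to the serious criteria includes the new one, and align the Severity entry, which now rests seriousness on outcome or action alone.
3. In both the unexpected-reaction and SUSAR definitions, replace *and* with *or* between nature and severity, so that a departure in either is enough.

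The reporting clocks in Section 6.10 need no change, because they follow from the classification. The cost is one criterion, two aligned entries, one word in two places, and a few more expedited reports. The new criterion is a matter of judgement, so some variation between assessors will remain.
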